12 STATISTICAL AND ANALYTICAL PLANS

This section presents a summary of the planned analyses for this protocol. Statistical analysis details will be provided in the statistical analysis plan (SAP) and clinical pharmacologic analysis details will be provided in the clinical pharmacology analysis plan, both of which will be finalized before the clinical data lock for the study.

12.1 Sample Size

The primary and secondary objectives of the study are the evaluation of the long-term safety and tolerability, and long-term efficacy of VX-445/TEZ/IVA. This is an open-label study that will enroll subjects who complete the last Treatment Period visit in the parent study and meet eligibility criteria. The parent study is a Phase 3 Vertex study investigating VX-445/TEZ/IVA (Study 104). Approximately 250 subjects are expected to enroll in this open-label study.

12.2 Analysis Sets

The **Open-label All Subjects Set** is defined as all subjects who were enrolled (defined as subject having data in the clinical database) in the open-label study. This analysis set will be used for individual subject data listings and disposition summary tables unless otherwise specified.

The **Open-label Full Analysis Set (OL-FAS)** is defined as all enrolled subjects who have received at least 1 dose of study drug in the open-label study. The OL-FAS will be used to summarize subject demographics and baseline characteristics and for all efficacy analyses unless otherwise specified.

The **Open-label Safety Set (OL-SS)** is defined as all subjects who have received at least 1 dose of study drug in the open-label study. The OL-SS will be used for all safety analyses unless otherwise specified.

12.3 Statistical Analysis

12.3.1 General Considerations

Continuous variables will be summarized using the following descriptive summary statistics: the number of subjects (n), mean, SD, median, minimum value (min), and maximum value (max). The precision of the measurement for each continuous variable will be specified in the SAP. Unless otherwise specified, min and max values will be reported with the same precision as

the units of the raw data. The mean, median, and SD will be reported to 1 additional decimal place. Any values that require a transformation to standard units (metric or SI) will be converted with the appropriate precision.

Categorical variables will be summarized using counts and percentages. Percentages will be presented to 1 decimal place.

The baseline value, unless otherwise specified, for the long-term safety analysis will be the most recent non-missing measurement (scheduled or unscheduled) collected before the first dose of VX-445/TEZ/IVA either in the parent study or the open-label study, as applicable. The baseline value for the long-term efficacy analysis will be defined as the most recent non-missing measurement (scheduled or unscheduled) collected before the first dose of study drug in the parent study. For assessments collected in duplicate or triplicate, the baseline will be defined as the average of non-missing values.

Baseline characteristics of subjects in the open-label study will be the same as the baseline characteristics in the parent study.

Change (absolute change) from baseline will be calculated as post-baseline value - baseline value.

The **Efficacy Analysis Period** in the open-label study will include the time from the first dose of study drug in the open-label study to the last scheduled efficacy visit in the open-label study, unless otherwise specified.

The **Treatment-emergent (TE) Period** in the open-label study will include the time from the first dose of study drug in the open-label study to 28 days after the last dose of the study drug in the open-label study or to the completion date of study participation (as defined in Section 9.1.5), whichever occurs first.

The long-term efficacy analysis will be performed by parent study for the Efficacy Analysis Period in the open-label study.

In general, long-term safety analyses will be performed in a pooled fashion.

12.3.2 Background Characteristics

12.3.2.1 Subject Disposition

Subject disposition will be summarized for the Open-label All Subjects Set. The number and percentage of subjects in the following categories for the open-label study will be summarized as appropriate:

- Open-label All Subjects Set
- Dosed (OL-SS)
- Enrolled and dosed (OL-FAS)
- Completed Treatment Period
- Prematurely discontinued treatment and the reasons for discontinuation
- Completed study
- Prematurely discontinued the study and the reasons for discontinuation

12.3.2.2 Demographics and Baseline Characteristics

Demographics, background (e.g., medical history), and baseline characteristics will be summarized by descriptive summary statistics. Baseline characteristics will be the same as the parent study baseline characteristics.

The following demographics and baseline characteristics will be summarized for the OL-FAS and will include (but not limited to) sex, race, ethnicity, baseline age, baseline weight, baseline height, baseline BMI, baseline ppFEV₁, baseline SwCl, and baseline score of CFQ-R RD.

Medical history will be summarized by MedDRA System Organ Class (SOC) and Preferred Term (PT) for the OL-FAS.

12.3.2.3 Prior and Concomitant Medications

Medications will be coded using the World Health Organization-Drug Dictionary and categorized as follows:

- **Prior medication:** any medication that was administered during the 56 days before the first dose of study drug in the open-label study
- **Concomitant medication:** medication continued or newly received during the TE Period in the open-label study
- **Post-treatment medication:** medication continued or newly received after the TE Period in the open-label study

A given medication may be classified as a prior medication, a concomitant medication, or a post-treatment medication; both prior and concomitant; both concomitant and post-treatment; or prior, concomitant, and post-treatment. If a medication has a missing or partially missing start/end date or time and if it cannot be determined whether it was taken before initial dosing in the open-label study, concomitantly during the TE Period in the open-label study, or beyond the TE Period in the open-label study, it will be considered in all 3 categories of prior, concomitant, and post-treatment medication.

Prior medications and concomitant medications will be summarized descriptively by Preferred Name based on the OL-FAS. Post-treatment medications will be provided separately in an individual subject data listing.

12.3.2.4 Study Drug Exposure and Compliance

Study drug exposure will be summarized for the OL-SS in terms of treatment a subject received in the open-label study, defined as [(the last day of study drug in the open-label study – the first day of study drug in the open-label study) + 1 day], regardless of study drug interruption.

Study drug compliance will be summarized overall and by treatment group based on the OL-FAS, and will be calculated as: $100 \times [1 - (\text{total number of days of study drug interruption in the open-label study}) / (\text{duration of study drug exposure in days in the open-label study})]$. A study drug interruption on a given day is defined as an interruption of any study drug on that day.

In addition, percentage of tablets taken in the open-label study will also be summarized overall and by treatment group based on the OL-FAS, and will be calculated as $100 \times [(\text{total number of tablets dispensed in the open-label study}) - (\text{total number of tablets returned in the open-label study}) / (\text{total number of tablets dispensed in the open-label study})]$.

study)] / (total number of tablets planned to be taken per day × duration of study drug exposure in days for the open-label study).

12.3.2.5 Important Protocol Deviations

An important protocol deviation (IPD) is a deviation that may significantly affect the completeness, accuracy, or reliability of the study data or that may significantly affect a subject's rights, safety, or well-being. The rules for identifying an IPD in the open-label study will be described in the SAP.

All IPDs will be provided in an individual subject data listing, and summarized, as appropriate.

12.3.3 Efficacy and Pharmacodynamic Analyses

The secondary objectives of the study are the evaluation of the long-term efficacy and PD of VX-445/TEZ/IVA.

12.3.3.1 Analysis of Primary Endpoint

Not applicable since efficacy and PD are not primary objectives.

12.3.3.2 Analysis of Secondary Efficacy Endpoints

The secondary endpoints include:

- **Absolute change in ppFEV₁**

One of the secondary efficacy endpoints is the absolute change in ppFEV₁ at visits in the open-label study, for subjects who receive at least 1 dose of study drug in the open-label study. The primary analysis for this secondary endpoint will be based on a mixed-effects model for repeated measures (MMRM), with the absolute change from baseline in ppFEV₁ as the dependent variable for visits in the open-label study. The model will be similar to the one used for the primary efficacy analysis in the parent study.

The details including sensitivity analyses and supportive analyses will be described in the SAP.

- **Absolute change in SwCl**

Analysis of this PD endpoint will be based on an MMRM similar to the analysis of the absolute change in ppFEV₁.

- **Absolute change in BMI**

Analysis of this endpoint will be based on an MMRM similar to the analysis of the absolute change in ppFEV₁.

- **Absolute change in BMI z-score**

Analysis of this endpoint will be based on an MMRM similar to the analysis of the absolute change in ppFEV₁.

- **Absolute change in body weight**

Analysis for this endpoint will be based on an MMRM similar to the analysis of the absolute change in ppFEV₁.

- **Absolute change in CFQ-R RD score**

Analysis of this endpoint will be based on an MMRM similar to the analysis of the absolute change in ppFEV₁.

12.3.3.3 Analysis of Exploratory Efficacy Endpoints

Exploratory efficacy endpoints include:

- **Absolute change in CFQ-R non-RD scores**

Analysis of this endpoint will be based on an MMRM similar to the analysis of the absolute change in ppFEV₁. Additional details will be specified in the SAP.

12.3.3.4 Multiplicity Adjustment

Not applicable

12.3.4 Safety Analysis

The primary objective of the study is the evaluation of the long-term safety and tolerability of VX-445/TEZ/IVA. All safety analyses will be based on the TE Period in the open-label study for subjects in the OL-SS.

The overall long-term safety profile of study drug will be assessed in terms of the following safety and tolerability endpoints:

- Incidence of treatment-emergent AEs (TEAEs)
- Clinical laboratory values (i.e., serum chemistry, hematology, coagulation, and urinalysis)
- ECGs
- Vital signs
- Pulse oximetry

In general, long-term safety analysis will be performed in a pooled fashion. All safety data will be presented in individual subject data listings. Only a descriptive analysis of safety data will be performed.

12.3.4.1 Adverse Events

For analysis purposes, AEs will be classified as pretreatment AEs, TEAEs, or post-treatment AEs, defined as follows:

- **Pretreatment AE:** any AE that occurred before the first dose of VX-445/TEZ/IVA in the TE Period in the open-label study
- **TEAE:** any AE that worsened (either in severity or seriousness) or newly developed at or after the first dose date of VX-445/TEZ/IVA in the TE Period in the open-label study
- **Post-treatment AE:** any AE that worsened (either in severity or seriousness) or newly developed after the TE Period in the open-label study

For AEs with missing or partial start dates, if there is no clear evidence that the AEs started before or after study drug treatment, then the AEs will be classified as TEAEs.

AE summary tables will be presented for TEAEs only and will include the following:

- All TEAEs
- TEAEs by strongest relationship
- TEAEs by maximum severity
- TEAEs leading to treatment discontinuation
- TEAEs leading to treatment interruption
- Serious TEAEs
- TEAEs leading to death
- Grade 3 and Grade 4 TEAEs
- Frequently reported TEAEs

Summaries will be presented by MedDRA SOC and PT using frequency counts and percentages (i.e., number and percentage of subjects with an event). When summarizing the number and percentage of subjects with an event, subjects with multiple occurrences of the same AE or a continuing AE will be counted once. Only the maximum severity level will be presented in the severity summaries, and the strongest relationship level will be presented in the relationship summaries. An AE overview table will be provided. In addition, a listing containing individual subject level AE data for all deaths and other serious and significant AEs will be provided separately. All AEs, including pre- and post-treatment AEs, will be presented in individual subject data listings.

Exposure-adjusted event rates may also be provided.

12.3.4.2 Clinical Laboratory Assessments

For the TE laboratory measurements, the observed values and change from baseline values of the continuous laboratory parameters will be summarized in SI units for the pooled population at each time point during the TE Period in the open-label study.

The number and percentage of subjects with at least 1 threshold analysis event during the TE Period in the open-label study will be summarized. The shift of the threshold analysis criteria from baseline to post-baseline will also be summarized for selected laboratory parameters. The threshold analysis and parameter selection criteria will be provided in the SAP.

Results of urinalysis and pregnancy tests will be listed in individual subject data listings only. In addition, a listing containing individual subject laboratory assessment values will be provided. This listing will include data from scheduled and unscheduled time points.

Additional safety laboratory data analyses may be described in the SAP.

12.3.4.3 Electrocardiogram

For the TE ECG measurements, a summary of observed values and change from baseline values will be provided at each time point during the TE Period in the open-label study, for the following standard 12-lead ECG interval measurements (in msec): RR, PR, QT, QTc for heart rate (HR) interval (QTcF), QRS duration, and HR (beats per minute [bpm]).

The number and percentage of subjects with at least 1 threshold analysis event during the TE Period in this open-label study will be summarized. The threshold analysis criteria will be provided in the SAP.

Additional ECG analyses may be described in the SAP.

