12.3.4.4 Vital Signs

For the TE vital signs measurements, the observed values and change from baseline values will be summarized at each time point during the TE Period in the open-label study. The following vital signs parameters will be summarized: systolic and diastolic blood pressure (mm Hg), temperature (°C), pulse rate (bpm), and respiratory rate (breaths per minute).

The number and percentage of subjects with at least 1 threshold analysis event during the TE Period in the open-label study will be summarized. The threshold analysis criteria will be provided in the SAP.

Additional vital signs analyses may be described in the SAP.

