9.4.3 Electrocardiogram

For the following ECG measurements during the TE period for Part A for OL-SS for Part A, a summary of observed values and change from baseline values will be provided for overall (“Any ELX/TEZ/IVA”) at each visit (in ms): RR interval, PR interval, QT interval, QTcF(QT corrected for HR), QRS duration, and Heart Rate (beats per minute).

The number and percentage of subjects meeting at least 1 threshold analysis criterion during the TE period for Part A for OL-SS for Part A will be summarized for overall (“Any ELX/TEZ/IVA”). The threshold analysis criteria are provided in Section 12.4.

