Parameter	Threshold Analysis	Comments
Reticulocytes/Erythrocytes (%)	<LLN >ULN	No CTCAE
Coagulation		
Activated partial thromboplastin time (PTT)	>ULN – ≤ 1.5×ULN >1.5× – ≤ 2.5×ULN >2.5×ULN	CTCAE grade 1-3
Prothrombin time (PT) International Normalized Ratio (INR)	>ULN – ≤ 1.5×ULN >1.5× – ≤ 2.5×ULN >2.5×ULN	CTCAE grade 1-3

Table 12-4 Threshold Analysis Criteria for Laboratory Tests (for labeling purpose)

Parameter	Threshold Analysis	Comments
Clinical Chemistry (LFT)		
ALT or AST	>3×ULN >5×ULN >8×ULN	For labeling purpose

Table 12-5 Threshold Analysis Criteria for ECGs

Parameter	Threshold Analysis	Comments
HR	Bradycardia <50 bpm <45 bpm Decrease from baseline ≥10 bpm Decrease from baseline ≥20 bpm <50 bpm and decrease from baseline ≥10 bpm <50 bpm and decrease from baseline ≥20 bpm	Per HV grade 2, 3, plus shift change
	Tachycardia >100 bpm >115 bpm >130 bpm Increase from baseline ≥10 bpm Increase from baseline ≥20 bpm >100 bpm and increase from baseline ≥10 bpm >100 bpm and increase from baseline ≥20 bpm	
PR	≥240 ms ≥300 ms ≥200 ms and increase from baseline ≥40 ms ≥200 ms and increase from baseline ≥100 ms	

Table 12-5 Threshold Analysis Criteria for ECGs

Parameter	Threshold Analysis	Comments
QRS	>110 ms >160 ms Increase from baseline \geq 20 ms Increase from baseline \geq 40 ms	
QTc Borderline Prolonged* Additional	>450 ms and <500ms (Male); >470 ms and <500ms (Female) \geq 500 ms Increase from baseline Increase from baseline >10 ms Increase from baseline >20 ms Increase from baseline >40 ms Increase from baseline >60 ms	To be applied to any kind of QT correction formula.

Note: Based on CPMP 1997 guideline.

Table 12-6 Threshold Analysis Criteria for Vital Signs

Parameter	Threshold Analysis	Comments
Pulse Rate	Same as above in ECG category	
SBP increased	>140 mmHg >160 mmHg >10 mmHg increase from baseline >20 mmHg increase from baseline >140 mmHg & >10 mmHg increase from baseline >140 mmHg & >20 mmHg increase from baseline >160 mmHg & >10 mmHg increase from baseline >160 mmHg & >20 mmHg increase from baseline	809/770 analyses
SBP decrease	<90 mmHg <80 mmHg >10 mmHg decrease from baseline >20 mmHg decrease from baseline <90 mmHg and >10 mmHg decrease from baseline <90 mmHg and >20 mmHg decrease from baseline <80 mmHg and >10 mmHg decrease from baseline <80 mmHg and >20 mmHg decrease from baseline	Per HV grade 1, 3, plus shift change

Table 12-6 Threshold Analysis Criteria for Vital Signs

Parameter	Threshold Analysis	Comments

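### Laboratory, QRS and absolute QTc threshold counts do not check the TC safety baseline, so they mix pre-existing with new abnormalities

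*Protocol*

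**What the plan says.** The protocol sets one counting rule and defers the limits. For ECG, the rule reads: "subjects with at least 1 threshold analysis event during the TE Period in this open-label study will be summarized", so one event in the period is enough for a subject to be counted. The limits are left for later: "The threshold analysis criteria will be provided in the SAP". Protocol 12.3.4.4 uses the same rule for vital signs.

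SAP 9.4.3 carries the rule over. What it reports, for the pooled group, is: "The number and percentage of subjects meeting at least 1 threshold analysis criterion during the TE period". SAP 9.4.2 does the same for laboratory values. Under the ECG derivation in SAP 12.1, every ECG value enters the threshold analysis, including repeats on one day.

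The limits are in SAP 12.4:

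- **Laboratory (Tables 12-3 and 12-4):** all are multiples of ULN, comparisons with LLN or ULN, or fixed values. None refers to baseline. The only baseline link is a threshold shift, which "will also be summarized for selected laboratory parameters". Protocol 12.3.4.2 says that the SAP will give the selection criteria, but SAP 9.4.2 and 12.4 neither give them nor name the parameters.
- **Heart rate and PR (Table 12-5):** combined rows exist, for example "<50 bpm and decrease from baseline ≥10 bpm".
- **QRS and QTc (Table 12-5):** absolute rows and change rows stand apart, with no combined row. SAP 9.4.3 plans no ECG shift table.
- **Pulse rate, blood pressure and weight (Table 12-6):** combined rows for pulse rate and blood pressure; every weight row is a change from baseline.

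The TC safety baseline (SAP 9.1) is the last value before the first dose of study drug in the parent study for subjects who received the triple combination there, and before the first open-label dose otherwise.

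**The concern.** A subject whose QRS is 112 ms before and throughout treatment counts under QRS >110 ms. A subject whose GGT was above ULN before any triple-combination dose, and stays there, counts under the first GGT row. Neither has changed, yet both appear in a table for the treatment-emergent period.

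Laboratory values and ECGs are components of the primary endpoint. SAP 9.4.2 and 9.4.3 present them only for the overall group, so no control column shows the background rate. The subject's own baseline is the main reference left, and these rows do not use it.

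The plan uses baseline elsewhere. A treatment-emergent AE is "any AE that worsened (either in severity or seriousness) or newly developed at or after the first dose date" of the triple combination. Pulse oximetry gets a shift from baseline to the lowest value (SAP 9.4.5). Heart rate and PR get limit-plus-change rows. No reason is given for treating laboratory limits, QRS and QTc differently.

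**Working it through.** The documents state no figure on this point, so there is none to reproduce.

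**Step 1. Class each criterion in SAP 12.4.** The bare QTc line on increase from baseline is read as a heading, and PT/INR as one parameter.

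| Group | Criteria | Use change from baseline | Of these, combined with a limit | Absolute only |
|---|---|---|---|---|
| ECG | 27 | 16 | 6 | 11 |
| Vital signs and weight | 51 | 38 | 20 | 13 |
| Laboratory, Table 12-3 | 82 | 0 | 0 | 82 |
| Laboratory, Table 12-4 | 3 | 0 | 0 | 3 |

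Of the 11 absolute-only ECG rows, 5 are heart rate and 2 are PR, which have combined companions. The other 4 (QRS >110 and >160 ms, and two absolute QTc categories) have none. All 13 absolute-only vital-sign rows have combined companions.

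**Step 2. Can the separate QRS rows stand in for a combined row?** Take two hypothetical subjects. One goes from 108 to 112 ms, a rise of 4 ms. This is a new crossing of 110 ms, but it meets neither change row (≥20, ≥40 ms). The other goes from 112 to 133 ms, a rise of 21 ms. This meets the ≥20 ms row and the >110 ms row but is not a new crossing. Two separate counts therefore cannot show how many subjects newly crossed the limit. The same logic holds for QTc.

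**Step 3. Simple count.** N = 250 is the expected enrolment. Assume a share p abnormal at baseline who stay abnormal, and new onset q = 2% among the rest. Neither is in the documents.

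- Counted: N × [p + (1 − p) × q]. New only: N × (1 − p) × q.
- p = 1%: 7.45 counted, 4.95 new.
- p = 5%: 250 × (0.05 + 0.95 × 0.02) = 17.25 counted, 4.75 new.
- p = 10%: 29.5 counted, 4.5 new.

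**Step 4. With visit-to-visit noise and no drug effect.** Let subject i have true mean m, within-subject SD s, and k later values. The chance that one value exceeds limit L is π = 1 − Φ((L − m)/s). The chance that any later value does is A = 1 − (1 − π)^k. The share of counted subjects already above L at baseline is E[πA] / E[A], averaged over a normal distribution of m. I evaluated this by numerical integration.

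QRS >110 ms, k = 8 (Day 15, Weeks 4, 8, 24, 48, 72, 96 and follow-up). Assumed mean 90-95 ms, between-subject SD 9-10, within-subject SD 3-4:

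| Mean / between SD / within SD | Above at baseline | Ever counted | Share of counted already above |
|---|---|---|---|
| 90 / 9 / 4 (lowest share) | 2.1% | 6.3% | 29% |
| 90 / 9 / 3 | 1.8% | 4.4% | 36% |
| 95 / 10 / 4 | 8.2% | 18.3% | 41% |
| 95 / 10 / 3 (highest share) | 7.5% | 14.6% | 49% |

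Laboratory limit at ULN, treated as open-ended, k = 11 treatment-period values (chemistry and haematology). Assumed baseline prevalence 5-30% and reliability 0.60-0.85, on a standardised scale:

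| Prevalence / reliability | Ever counted | Share of counted already above |
|---|---|---|
| 5% / 0.60 | 22.6% | 18% |
| 5% / 0.85 | 13.9% | 33% |
| 30% / 0.60 | 71.1% | 41% |
| 30% / 0.85 | 53.7% | 55% |

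Adding the follow-up sample (k = 12) gives 18-54%. Coagulation has only 5 treatment-period samples; k = 5 gives 22-60%.

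**The case against.** **Other summaries give context.** Observed values and changes from baseline are shown at each visit. Individual laboratory values are listed. Some laboratory parameters get a shift table. Clinically significant worsening is recorded as an AE (Protocol 13.1.1.2) and then meets the new-or-worse rule. All of this stands, and it means that pre-existing abnormality is not wholly hidden. None of it gives the number of subjects newly crossing a limit for QRS, QTc or the unselected laboratory tests.

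**Most ECG and vital-sign criteria do use baseline.** A reader of the protocol sentence alone might infer that all ECG and vital-sign threshold counts ignore baseline. The documents do not support that: 16 of 27 ECG criteria and 38 of 51 vital-sign criteria involve change, and the protocol sends the reader to the SAP for them. A reader might also infer that most laboratory tests will have no shift table. That cannot be checked, because the selected parameters are not named.

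**Safety is descriptive.** No test, error rate or sample size depends on these counts, and the plan does not say that they are caused by the drug. This stands and limits the weight of the point.

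**The AE comparison is not exact.** Treatment-emergent AEs are judged from the first open-label dose. The TC safety baseline precedes the parent-study dose for subjects treated there, so a limit first crossed in Study 104 would count as new here. This stands too; it bears on how the added column is labelled.

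**Conclusion.** The point holds for the laboratory criteria in Tables 12-3 and 12-4 and for the four absolute QRS and QTc rows. On these, the planned counts combine abnormalities present before the first triple-combination dose with those that arose later, and no planned table separates them except for unnamed laboratory parameters.

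The size rests wholly on assumptions: 29-49% of counted subjects for QRS >110 ms and 18-55% for a laboratory limit at ULN, with no drug effect. Scaled to 250 subjects, the two extreme QRS cases are about 16 counted with 4 to 5 already above (250 × 6.3%; 29% of that), and about 36 counted with 18 already above (250 × 14.6%; 49% of that). The high laboratory limits, such as >8×ULN, were not modelled and may behave differently.

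This is a cheap and worthwhile improvement to a descriptive primary safety summary. It is not a flaw that invalidates the analysis. Heart rate, PR, pulse rate, blood pressure and weight need nothing further.

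**What to change.** Change SAP 9.4.2, 9.4.3 and 12.4 only. The protocol needs no edit because it defers the criteria to the SAP.

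1. Keep the existing any-value counts.
2. Beside each absolute-only laboratory, QRS and QTc row, add the number and percentage of subjects newly meeting that limit. The denominator is subjects with a non-missing TC safety baseline that met neither that limit nor a worse category.
3. Label the column as new since the TC safety baseline, so that crossings that began in Study 104 are not read as starting in this study.
4. Extend the baseline-to-worst threshold shift table to all Table 12-3 parameters, QRS and QTc. This also settles which laboratory parameters are selected.
5. Show subjects without a baseline on a separate line.

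The cost is SAP wording, programming and extra table columns; no new data are needed. The added count will not remove noise. In the QRS scenarios above, 3-12% of subjects below the limit at baseline would still cross it at some visit with no drug effect. The new count should therefore be read beside the per-visit changes.
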